4.3.2 Key Secondary Endpoint Estimand

The attributes of the estimand for the key secondary endpoint included in the multiplicity control procedure of this trial are:

- 1. Treatment regimens: ciclesonide and placebo
- 2. Populations of interest: patients meeting inclusion/exclusion criteria grouped according to randomized treatment assignment reflect the target population
- 3. Patient-level outcome: binary indicator of alleviation of COVID-19-related symptoms of cough, dyspnea, chills, feeling feverish, repeated shaking with chills, muscle pain, headache, sore throat, and new loss of taste or smell, defined as symptom-free for a continuous period of \geq 24 hours (ie, \geq 3 AM/PM assessments) by day 14
- 4. Intercurrent events: regardless of the use of rescue medications, protocol violations, or investigational product discontinuation
- 5. Population-level summary measure: difference in response probabilities between treatment regimens

The **treatment-policy strategy** for this estimand is the difference in probabilities of alleviation of COVID-19-related symptoms of cough, dyspnea, chills, feeling feverish, repeated shaking with chills, muscle pain, headache, sore throat, and new loss of taste or smell, defined as symptom-free for a continuous period of ≥ 24 hours (ie, ≥ 3 AM/PM assessments) by day 14 between those assigned to ciclesonide and those assigned to placebo, regardless of patient's use of rescue medications, protocol violations, or investigational product discontinuation. Therefore, for all patients in the ITT analysis set, all observed on-study data will be analyzed in accordance with the definition set forth above for intercurrent events.

Since death and hospitalization are not part of this key secondary endpoint patient level-outcome definition, a composite strategy will be used to handle these situations. If a patient dies or is hospitalized, then the value attributed in that scenario would be failure to achieve alleviation of COVID-19-related symptoms which ascribes the most unfavorable value.

Estimands for other secondary efficacy endpoints included in the multiplicity control procedure (section 10.7.3) will be described in the Statistical Analysis Plan (SAP).

5 STUDY DESCRIPTION

5.1 Study Design

This is a multicenter, randomized, double-blind, placebo-controlled, parallel-group, efficacy, and safety study of ciclesonide MDI for the treatment of symptomatic COVID-19 infection. Enrolled patients will be male and female adults and adolescents ≥ 12 years of age with confirmed COVID-19 infection who are currently exhibiting symptoms of the disease and who are not currently hospitalized or under immediate consideration for hospitalization at the time of enrollment. The study will consist of an initial screening/enrollment/randomization visit, a 30-day treatment period, and a follow-up period.

Following signature of the informed consent form (ICF), patients meeting inclusion/exclusion criteria will be randomly assigned (1:1) to treatment with ciclesonide MDI 320 µg BID (AM and PM) plus standard supportive care (hereafter referred to as the ciclesonide arm) or placebo MDI BID (AM and PM) plus standard supportive care (hereafter referred to as the placebo arm). During the initial screening/enrollment/randomization visit, patients will be instructed on how to self-administer a MDI and will be discharged home with a 30-day supply of investigational product (ie, either ciclesonide MDI or placebo MDI), standard supportive care, a pulse oximeter for at-home oxygen saturation level monitoring, and an electronic diary (eDiary). A nasopharyngeal sample for viral load analysis will also be obtained at the initial screening/enrollment/randomization visit. Patients will be instructed to record self-administration of investigational product and oxygen saturation levels in the eDiary. Prior to self-administration of the investigational product (ie, within 1 hour of administration), patients will also complete and record assessments in the eDiary of severity of COVID-19-related symptoms of cough, dyspnea, chills, and feeling feverish (based on a 4-point scale where 0 = absent, 1 = mild, 2 = moderate, and 3 = severe) and the presence/absence of COVID-19-related symptoms of repeated shaking with chills, muscle pain, headache, sore throat, and new loss of taste or smell. Qualified healthcare providers will contact patients on days 2, 4, 6, 8, 10, 12, 14, 21 ± 2 days, and 30 ± 2 days for a health status check, to collect adverse event and concomitant medication information, and to confirm/clarify information recorded in the eDiary. During these patient contacts, medical advice commensurate with standard of care for reported symptoms or adverse events will be provided. On day 30 (window of + 2 days), the patient will return to the study site for collection of a nasopharyngeal sample for viral load analysis and to return the eDiary and investigational product (ie, used and unused MDIs). Qualified healthcare providers will contact patients on day 37 ± 4 days and day 60 ± 7 days to collect follow-up safety and outcome data (the follow-up period).

Patients (or their representatives) will be asked to notify study personnel directly in the event they visit an emergency department or are hospitalized during their participation in the study.

Patient duration on study is expected to be approximately 60 days, including the screening/ enrollment/randomization visit, the 30-day treatment period and the subsequent follow-up period. In the event the patient requires hospitalization during the 30-day treatment period, the patient will discontinue investigational product and scheduled follow-up procedures but will continue to be followed for the outcome of hospitalization and ongoing adverse events (see section 5.3.4).

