| HCP to contact patient for health status check, to collect adverse event and concomitant medication information, and to confirm/clarify information recorded in eDiary ^e | | X (days 2, 4, 6, 8, 10, 12, 14, 21 ± 2 days, and 30 ± 2 days) | | |
| Return of eDiary and investigational product (ie, used and unused MDIs) | | X (day 30 [window of $+ 2 \text{ days}])^d$ | | Х |
| HCP to contact patient to collect follow-up safety and outcome data | | | X (day 37 ± 4 days and day 60 ± 7 days) | \mathbf{X}^{f} |
| AM = morning (prior to noon); BID = twice a day; COVID-19 = coronavirus disease 2019; eDiary = electronic diary; HCP = healthcare provider; IP = investigational | | | | |

product; MDI = metered-dose inhaler; PM = evening (prior to midnight); SARS-CoV-2 = Severe Acute Respiratory Syndrome Coronavirus 2.

- a^{a} = To include date of onset of COVID-19 symptoms.
- = To meet criteria for inclusion, patient must have a positive SARS-CoV-2 molecular or antigen diagnostic test within 72 hours prior to enrollment.
- ^c = Note on day 1 dosing: In the event the patient receives the initial dose of IP at or before noon during the screening/enrollment/randomization visit, this will be considered to be the day 1 AM dose and the patient will be instructed to perform symptom assessments and oxygen saturation level monitoring, and to self-administer the day 1 PM dose prior to midnight. In the event the patient receives the initial dose of IP any time after noon during the screening/enrollment/randomization visit, this will be considered to be the day 1 PM dose and the patient will be instructed to wait until morning to perform symptom assessments, oxygen saturation level monitoring, and to self-administer the next dose (ie, day 2 AM dose). Note on day 30 dosing: Patients will be instructed to continue dosing through day 30. In the event the patient has their day 30 (window of + 2 days) visit on day 30, they will be instructed to perform symptom assessments and oxygen saturation level monitoring, and to self-administer the day 30 doses as per their typical schedule/routine. Thus, depending upon the time of day that the day 30 visit occurs, patients may or may not receive both doses on day 30. For patients that have their day 30 visit on day 31 or day 32, they will be instructed to complete through the day 30 PM dose and then discontinue investigational product dosing, symptom assessments, and oxygen saturation level monitoring.

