 - = On day 30 (window of + 2 days) the patient will return to the study site for collection of a nasopharyngeal sample for viral load analysis and to return the eDiary and investigational product (ie, used and unused MDIs).
- = During these patient contacts, medical advice commensurate with standard of care for reported symptoms or adverse events will be provided.
- = In the event of early termination, all ongoing non-serious adverse events will be followed until resolution, stabilization, or study day 60, whichever comes first; all ongoing serious adverse events will be followed until resolution or resolution with sequelae.

Note: Patients (or their representatives) will be asked to notify study personnel directly in the event they visit an emergency department or are hospitalized during their participation in the study.

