5.3.4 Early Termination Procedures

In the event of early termination, all ongoing non-serious adverse events will be followed until resolution, stabilization, or study day 60, whichever comes first; all ongoing serious adverse events will be followed until resolution or resolution with sequelae. Patients should be instructed to return the eDiary and investigational product (ie, used and unused MDIs) to the study site in a timely manner.

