7 STUDY ASSESSMENTS AND PROCEDURES

7.1 Efficacy

7.1.1 Efficacy Endpoints

The primary efficacy endpoint is:

• Time to alleviation of COVID-19-related symptoms of cough, dyspnea, chills, feeling feverish, repeated shaking with chills, muscle pain, headache, sore throat, and new loss of taste or smell, defined as symptom-free for a continuous period of ≥ 24 hours (ie, ≥ 3 AM/PM assessments) by day 30

The secondary efficacy endpoints for the study are:

- Percentage of patients with hospital admission or death by day 30
- All-cause mortality by day 30
- COVID-19-related mortality by day 30
- Percentage of patients with subsequent emergency department visit or hospital admission for reasons attributable to COVID-19 by day 30
- Percentage of patients with alleviation of COVID-19-related symptoms of cough, dyspnea, chills, feeling feverish, repeated shaking with chills, muscle pain, headache, sore throat, and new loss of taste or smell, defined as symptom-free for a continuous period of ≥ 24 hours (ie, ≥ 3 AM/PM assessments) by day 7, by day 14, and by day 30
- Time to hospital admission or death
- Change from baseline in oxygen saturation levels
- Change from baseline in COVID-19 viral load in nasopharyngeal sample at day 30

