9.3 Serious Adverse Event Definition

A serious adverse event is any untoward medical occurrence that, at any dose:

- Results in death
- Is life-threatening
- Requires patient hospitalization or prolongation of existing hospitalization
- Results in persistent or significant disability and/or incapacity
- Results in a congenital anomaly or birth defect

The term "life-threatening" in the definition of "serious" refers to an event in which the patient was at immediate risk of death at the time of the serious adverse event. It does not refer to a serious adverse event that hypothetically might have caused death if it were more severe.

Medical and scientific judgment should be exercised in deciding whether expedited reporting is appropriate in other situations, such as important medical events that may not be immediately life-threatening or result in death or hospitalization, but may jeopardize the patient or may require intervention to prevent one of the other outcomes listed in the definition above. These should also be considered to be serious adverse events.

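### After a hospital admission no day 30 vital-status check is clearly required, so a death by day 30 that follows recorded resolution of the event may not be ascertained

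*Combined protocol and SAP*

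**What the plan says.** **Follow-up after admission.** For an admission in the 30-day treatment period, section 5.1 states that "the patient will discontinue investigational product and scheduled follow-up procedures but will continue to be followed for the outcome of hospitalization" and for ongoing adverse events. It then points to section 5.3.4. The synopsis repeats the rule.

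**Early termination.** Section 5.3.4 concerns events that are already open. For non-serious events, "all ongoing non-serious adverse events will be followed until resolution, stabilization, or study day 60, whichever comes first". For serious events, "all ongoing serious adverse events will be followed until resolution or resolution with sequelae". Footnote f of Table 1 carries the same text.

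**Table 1.** The row "HCP to contact patient to collect follow-up safety and outcome data" is scheduled for days 37 and 60. It is also marked in the Early Termination column, with footnote f and no day. The row of health-status contacts that ends on day 30 has no Early Termination entry.

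**Serious adverse events.** Under section 9.3 an event is serious if it "Requires patient hospitalization or prolongation of existing hospitalization", or if it results in death. Section 9.4 requires reporting regardless of causality until the patient completes or discontinues the study. After that, it requires a report only if the investigator learns of the event and suspects a relation to product.

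**Endpoints.** Section 7.1.1 lists "All-cause mortality by day 30" and its COVID-19-related counterpart. Section 10.2 analyses efficacy in all randomised patients, and section 10.7.3 places the two mortality endpoints tenth and eleventh in the test sequence.

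**Missing data.** Section 10.3.2 makes sensitivity analyses optional. The tipping-point analysis in section 10.7.1 is for the primary endpoint only.

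**The concern.** A mortality endpoint with a fixed date needs vital status at that date for everyone in the analysis set. Here the rule that takes patients off the contact schedule is triggered by admission, and admitted patients are plausibly those at highest risk of death. Admission is also an outcome that treatment is meant to change, so any gap in ascertainment could differ between arms.

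If a patient recovers from the admission, the event is closed, and the patient then dies at home before day 30, it is not clear that any required contact would find the death. Section 5.1 asks patients or their representatives to report emergency visits and hospitalisations, but does not name death. At stake are the two mortality endpoints and, secondarily, new adverse events after discharge, because the day 37 and day 60 safety contacts are also scheduled follow-up.

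**Working it through.** **Step 1. Which deaths does the written rule reach?**

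| Death by day 30 | Captured? | Basis |
|---|---|---|
| In hospital | Yes | Section 5.1, outcome of hospitalisation |
| After discharge, serious event still open | Yes | Sections 5.3.4 and 9.4, followed to resolution |
| After the event is recorded as resolved | Not assured | No day 30 entry under Early Termination; footnote f covers ongoing events only |

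Only the third row is a gap.

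**Step 2. Which endpoints are exposed for an admitted patient?**

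- Primary endpoint and day 14 alleviation (tests 1 and 2): not exposed. Sections 4.3.1 and 4.3.2 set admission to failure.
- Emergency visit or admission attributable to COVID-19 (test 7): already an event if the admission was for COVID-19.
- Time to, and percentage with, admission or death (tests 8 and 9): the admission is already the event.
- All-cause and COVID-19-related mortality (tests 10 and 11): exposed.

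**Step 3. How many deaths?** The plan gives no admission rate, death rate or power for mortality, so there is no mortality figure to reproduce. Its sample-size figure concerns the primary endpoint: 4 × (1.960 + 1.282)² / (ln 1.58)² gives the stated 201 events at two-sided 0.05 and 90% power. This point does not alter that figure. The only plan input used below is N = 400 (section 10.1). The rates are assumptions.

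Admitted = 400 × h. Expected deaths after discharge by day 30 = 400 × h × d. Chance of at least one = 1 − (1 − d)^(400h).

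| h (admitted) | d (die after discharge) | Admitted | Expected deaths | Chance of at least one |
|---|---|---|---|---|
| 3% | 1% | 12 | 0.12 | 11% |
| 3% | 5% | 12 | 0.60 | 46% |
| 5% | 1% | 20 | 0.20 | 18% |
| 5% | 5% | 20 | 1.00 | 64% |
| 10% | 1% | 40 | 0.40 | 33% |
| 10% | 5% | 40 | 2.00 | 87% |

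These are deaths exposed to the gap, not deaths missed. For given h and d they are an upper limit, because a death while the event is still open is followed anyway.

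**Step 4. Can one death matter?** Fisher's exact test, standing in for the planned logistic regression, gives p = 0.030 for 0 against 6 deaths with 200 per arm. If one of the six is not found, 0 against 5 gives p = 0.061. Power for mortality is low in any case: about 13% for 2% against 1%, and 37% for 5% against 2% (assumed rates).

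**The case against.** The strongest reply is that the protocol does keep admitted patients in view. Admission is a serious adverse event, followed to resolution with no day limit, and discharge is not defined as resolution. Admission is not among the withdrawal reasons in section 6.4. If an admitted patient has not discontinued the study, section 9.4 still requires any death to be reported regardless of causality. Table 1 also marks an outcome contact under Early Termination, separately from the adverse-event row. If footnote f confined that contact to ongoing adverse events, the second row would add nothing.

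Much of this stands. A reader might infer that follow-up ends at discharge and that later deaths are simply missed; the documents do not say so. They are ambiguous. Section 5.1 stops scheduled procedures and sends the reader to early-termination rules, which leaves the patient's study status unclear. The outcome contact has no day, and its footnote describes only open events. No section requires vital status at day 30.

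Three further inferences also lack support.

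- **Conflict with the treatment-policy strategy.** That strategy is defined only for the primary and day 14 symptom estimands (sections 4.3.1 and 4.3.2), where admission is handled by a composite strategy. Estimands for the other tested endpoints are left to the SAP.
- **Uncontacted patients counted as alive.** No rule for unknown vital status is given, in either direction.
- **Established bias between arms.** Differential loss is possible, but nothing in the documents shows it.

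**Conclusion.** The point holds in a limited form. Following the rule as written can leave a death by day 30 unascertained once the serious adverse event has been recorded as resolved, and sections 5.1 and 5.3.4, Table 1 and footnote f do not agree clearly enough to exclude this.

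For admitted patients the efficacy effect is essentially confined to the last two of eleven tests, which are reached formally only if the nine before them succeed. The primary endpoint is not affected. On the assumed rates, about 0.1 to 2 deaths are exposed in the whole trial. That is small in number but can be large relative to a rare endpoint. The range rests entirely on assumed admission and post-discharge death rates. The textual gap does not depend on them.

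**What to change.** - Reconcile sections 5.1 and 5.3.4, the Early Termination column of Table 1, and footnote f.
- State that every randomised patient who has not withdrawn consent, including those hospitalised or terminated early, keeps the scheduled day 30 contact to record vital status, cause of death, and emergency or hospital use. Preferably keep the day 37 and day 60 safety contacts too. Patients terminated early without an admission belong in this rule because section 5.3.4 governs them as well, and their later admissions or deaths bear on tests 7 to 9.
- State in the SAP how unknown day 30 vital status is handled in the two mortality analyses.

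The cost is wording and a few phone contacts, already in the schedule, for a small number of patients. No visit or procedure is added, and the sample size does not change. The rule on investigational product after admission is outside this point.

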5.2 Study Schedule

The time and events schedule for this study is provided in Table 1.

| Table 1.Schedule of Events | | | | |
|--|--|--|---------------------------------------|----------------------|
| | Screening/Enrollment/Randomization Visit (Day 1) | Treatment Period (Day 1 through Day 30) | Follow-up Period (Through Day 60) | Early Termination |
| Informed consent | X (before administration of any study-specific procedures) | | | |
| Inclusion/exclusion criteria review | X (predose) | | | |
| Prior/concomitant medication review | X (predose) | X (collected during patient contacts) | | |
| Demographic data and medical history ^a | X (predose) | | | |
| Physical examination, vital signs, height, weight, and calculation of body mass index | X (predose) | | | |
| Urine pregnancy test (for females of childbearing potential only) | X (predose, within 48 hours prior to enrollment) | | | |
| Confirm positive COVID-19 diagnostic test ^b | X (predose) | | | |
| Randomization | X (predose) | | | |
| Dispensing of IP, eDiary, and pulse oximeter | X (predose) | | | |
| Training on MDI inhalation technique (including rinsing of mouth with water following inhalation of IP), use of eDiary, and use of pulse oximeter | X (predose) | | | |
| Assess severity of COVID-19-related symptoms of cough, dyspnea, chills, and feeling feverish using a 4-point scale | X (predose) | X (BID [AM and PM] \leq 1 hour prior to IP administration, record in eDiary) ^c | | |
| Assess presence/absence of COVID-19- related symptoms of repeated shaking with chills, muscle pain, headache, sore throat, and new loss of taste or smell | X (predose) | X (BID [AM and PM] \leq 1 hour prior to IP administration, record in eDiary) ^c | | |
| Oxygen saturation levels | X (predose) | X (BID [AM and PM] \leq 1 hour prior to IP administration, record in eDiary) ^c | | |
| Collection of nasopharyngeal sample for viral load analysis | X (predose) | X (day 30 [window of $+ 2$ days]) ^d | | |
| IP administration | X | X (BID [AM and PM], record in eDiary) ^{c} | | |
| Adverse events | X (record any adverse events that occur following signing of informed consent) | X (collected during patient contacts) | X (collected during patient contacts) | X ^f |

| Table 1.Schedule of Events | | | | |
|---|---|--|--|----------------------|
| | Screening/Enrollment/Randomization Visit (Day 1) | Treatment Period (Day 1 through Day 30) | Follow-up Period (Through Day 60) | Early Termination |
| HCP to contact patient for health status check, to collect adverse event and concomitant medication information, and to confirm/clarify information recorded in eDiary ^e | | X (days 2, 4, 6, 8, 10, 12, 14, 21 ± 2 days, and 30 ± 2 days) | | |
| Return of eDiary and investigational product (ie, used and unused MDIs) | | X (day 30 [window of $+ 2 \text{ days}])^d$ | | Х |
| HCP to contact patient to collect follow-up safety and outcome data | | | X (day 37 ± 4 days and day 60 ± 7 days) | \mathbf{X}^{f} |
| AM = morning (prior to noon); BID = twice a day; COVID-19 = coronavirus disease 2019; eDiary = electronic diary; HCP = healthcare provider; IP = investigational | | | | |

product; MDI = metered-dose inhaler; PM = evening (prior to midnight); SARS-CoV-2 = Severe Acute Respiratory Syndrome Coronavirus 2.

- a^{a} = To include date of onset of COVID-19 symptoms.
- = To meet criteria for inclusion, patient must have a positive SARS-CoV-2 molecular or antigen diagnostic test within 72 hours prior to enrollment.
- ^c = Note on day 1 dosing: In the event the patient receives the initial dose of IP at or before noon during the screening/enrollment/randomization visit, this will be considered to be the day 1 AM dose and the patient will be instructed to perform symptom assessments and oxygen saturation level monitoring, and to self-administer the day 1 PM dose prior to midnight. In the event the patient receives the initial dose of IP any time after noon during the screening/enrollment/randomization visit, this will be considered to be the day 1 PM dose and the patient will be instructed to wait until morning to perform symptom assessments, oxygen saturation level monitoring, and to self-administer the next dose (ie, day 2 AM dose). Note on day 30 dosing: Patients will be instructed to continue dosing through day 30. In the event the patient has their day 30 (window of + 2 days) visit on day 30, they will be instructed to perform symptom assessments and oxygen saturation level monitoring, and to self-administer the day 30 doses as per their typical schedule/routine. Thus, depending upon the time of day that the day 30 visit occurs, patients may or may not receive both doses on day 30. For patients that have their day 30 visit on day 31 or day 32, they will be instructed to complete through the day 30 PM dose and then discontinue investigational product dosing, symptom assessments, and oxygen saturation level monitoring.
 - = On day 30 (window of + 2 days) the patient will return to the study site for collection of a nasopharyngeal sample for viral load analysis and to return the eDiary and investigational product (ie, used and unused MDIs).
- = During these patient contacts, medical advice commensurate with standard of care for reported symptoms or adverse events will be provided.
- = In the event of early termination, all ongoing non-serious adverse events will be followed until resolution, stabilization, or study day 60, whichever comes first; all ongoing serious adverse events will be followed until resolution or resolution with sequelae.

Note: Patients (or their representatives) will be asked to notify study personnel directly in the event they visit an emergency department or are hospitalized during their participation in the study.

